### **I. Introductory Background:**

Pregnancies associated with diabetes mellitus are accompanied by high risks of adverse maternal and fetal outcomes. Uncontrolled glucose levels in pregnancy can lead to fetal loss (miscarriage, stillbirth), congenital malformations, preterm delivery, cesarean section, macrosomia, neonatal hypoglycemia, and the like. Given these high risks, the American Diabetes Association (ADA) recommends rigorous glucose control throughout gestation with a glycated hemoglobin A1C (A1C) of <6% for women with preexisting diabetes. The strict glycemic targets are especially difficult to achieve for women dependent on insulin throughout gestation, such as those with Type 1 Diabetes (T1D). Their rates of severe hypoglycemia (SH, hypoglycemia requiring 3rd party assistance) are critically high. Strategies are needed to optimize glucose control both pre- and postprandially without significantly increasing the risk of hypoglycemia throughout gestation. Closed-loop (CL) insulin therapy employs a continuous subcutaneous insulin infusion pump with feedback from a continuous glucose monitor (CGM). Several CL systems evaluated in non-pregnant populations have been found to improve glucose control. One of these Hybrid CL (HCL) systems was recently approved by the Federal Drug Administration (FDA) and has been evaluated in non-pregnant adolescents and adults. In this proposal, we aim to improve maternal and fetal health through a novel insulin delivery system, and to obtain pilot data to ultimately reduce birth complications.

The effects of CL therapy on glucose and pregnancy outcomes are largely unknown. Only one investigational CL system has been studied in women with diabetes throughout most of pregnancy. This single hormone HCL system was found to increase the glucose target time in range (TIR) compared to sensor-augmented pump therapy (SAPT), however rates of large-for-gestational age (LGA) infants remained high. There is currently one HCL system on the market approved by the FDA, the Medtronic 670G system with the Guardian sensor. The 670G system can be used in auto, closed mode (HCL therapy) or manual, open mode (SAPT) using the same insulin pump and continuous glucose monitor, offering a unique opportunity to compare therapies with the same devices. Women across the United States are beginning to use this HCL therapy, which has never been studied in pregnancy. As rates of unintended pregnancy remain high in the United States (~45%), many women may be using the 670G without knowing they are pregnant for many weeks. Thus, it is critical that we understand how this system will perform throughout pregnancy with regards to safety, glucose control, quality of life, and maternal and fetal outcomes in comparison to SAPT therapy.

### **II. Hypotheses and Specific Aims:**

The PICLS (Pregnancy Intervention with a Closed-Loop System) Study is a two-center, prospective, 'open-label', single-blind, investigator-initiated randomized controlled pilot

study evaluating hybrid closed-loop (HCL) insulin delivery among pregnant women with T1D compared with sensor-augmented pump therapy (SAPT) throughout gestation and the first 6 weeks of the post-partum period at the Barbara Davis Center for Diabetes and Ohio State University. The HCL system being used is the Medtronic 670G system, which has been FDA-approved in non-pregnant populations but has never been studied in pregnancy.

**Specific Aim (SA) 1:** Evaluate safety of HCL therapy (Medtronic 670G with Guardian sensor) compared to SAPT in women with T1D throughout the 2nd and 3rd trimesters of gestation and the early post-partum period.

**Hypothesis SA 1.1:** We hypothesize that time spent with glucose <54 mg/dL will be the same or reduced among women using the HCL system compared to those using SAPT.

**Hypothesis SA 1.2:** We hypothesize that the episodes of diabetic ketoacidosis and rates of adverse skin reactions will be similar between groups.

**Specific Aim 2:** Evaluate indices of glucose control and fear of hypoglycemia in pregnant women with T1D using HCL therapy compared to those using SAPT throughout the 2nd and 3rd trimesters of gestation and in the early post-partum period.

**Hypothesis SA 2.1:** We hypothesize that HCL therapy will increase time spent in the glucose target range (63-140 mg/dL), reduce time spent in mild and more severe hypoglycemia (<63 mg/dL and <54 mg/dL, respectively), and reduce time spent in hyperglycemia (>140 mg/dL) over time compared to SAPT.

**Hypothesis SA 2.2:** We hypothesize that HCL therapy will reduce fear of hypoglycemia as measured by the Hypoglycemia Fear Survey, starting in the 1st trimester of pregnancy compared to SAPT.

**Specific Aim 3:** Evaluate quality of life and device acceptability in pregnant women with T1D using HCL therapy compared to those using SAPT throughout the 2nd and 3rd trimesters of gestation and in the early post-partum period.

**Hypothesis SA 3.1:** We hypothesize that pregnant women with T1D randomized to HCL therapy or SAPT will report similar quality of life (general mental health and general health perceptions), as measured by the Medical Outcomes Study (MOS) Short-Form 36 (SF-36), without a significant difference between groups.

**Hypothesis SA 3.2:** We hypothesize that HCL will be more acceptable to subjects than SAPT, as measured by Insulin Delivery Satisfaction Survey and the Glucose Monitoring Satisfaction Survey.

**Hypothesis SA 3.3:** We hypothesize that HCL in mid-pregnancy, late pregnancy, and post-partum will be more acceptable to subjects than SAPT in the first trimester in the same women using both modes of therapy, as measured by the INSPIRE Questionnaire.

**Specific Aim 4 (Exploratory Aim):** Evaluate maternal and fetal outcomes in pregnant women with T1D using HCL therapy compared to those using SAPT throughout gestation and in the early post-partum period.

**Hypothesis SA 4.1:** We hypothesize that rates of fetal loss, preeclampsia, cesarean section, and neonatal hypoglycemia will be similar between groups.

**Hypothesis SA 4.2:** We hypothesize that rates of large-for-gestational age infants and macrosomia (birth weight >4,000 grams) will be similar between groups.

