To address **Specific Aim 1**, we will compare percent of time spent in the SH range of <54 mg/dL on CGM (primary outcome) using a non-inferiority t-test with a margin of 1%. Counts of DKA and adverse skin reactions (secondary outcomes) will be compared between groups (HCL vs. SAPT) using t-tests for normally distributed variables and Wilcoxon Rank-Sum test for non-normal variables. As the purpose of this study is to demonstrate that HCL has a similar safety profile compared to SAPT during pregnancy, we will use a non-inferiority test. As a secondary analysis of events such as SH, DKA, and skin reactions, we will account for potential differential follow-up times due to miscarriage, drop-out, and withdrawal using Poisson regression with an offset for follow-up time. To address **Specific Aim 2**, we will compare CGM glucose variables (primary outcomes for glucose variables will be time spent <54, <63, 63-140, >140, >180 mg/dL; secondary outcomes will be glucose SD, J index, HBGI, LBG, MAGE, and CONGAn) and fear of hypoglycemia score between groups (HCL vs. SAPT) using t-tests for normally distributed variables and Wilcoxon Rank-Sum test for non-normally distributed variables. We will examine the buckets of time spent in each range (hypoglycemia, in range, and hyperglycemia) by day and night, as well as day-to-day variation. Mean glucose variables and hypoglycemia fear scores will be compared during each trimester of pregnancy and 4-6 weeks post-partum using mixed models. To address **Specific Aim 3**, we will compare SF-36 scores, insulin device satisfaction and glucose device satisfaction by group (HCL vs. SAPT) using t-tests if scores are normally distributed and Wilcoxon Rank-Sum test if scores are non-normal. We will analyze changes in INSPIRE Questionnaire scores over time in the HCL group. **Specific Aim 4** is an exploratory aim, and for this aim we will examine rates of fetal loss, preeclampsia, cesarean section, LGA, and neonatal hypoglycemia using Chi-square tests. We will account for potential differential follow-up times due to miscarriage, drop-out, and withdrawal using Poisson regression with an offset for follow-up time as a sensitivity analysis, in addition to the proposed chi-square tests in the exploratory analyses of fetal loss, preeclampsia, Caesarean section, LGA, and neonatal hypoglycemia. We will use mixed models to analyze changes in repeated measures, such as glycemia variables and hypoglycemia fear scores by trimester. We will evaluate the percent of time spent in closed loop by trimester as a feasibility outcome that is important to the next step of a larger clinical trial with efficacy outcomes.

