
For women who discontinue CGM therapy during the study, we will do an intention to treat analysis of above-stated outcomes. The alpha level will be 0.05 for all analyses, except the non-inferiority tests (alpha = 0.025). The use of mixed models and Poisson regression will allow for analysis of data for the portion of the study completed with CGM therapy.

**Power and Sample Size Calculations:** The primary outcome for **Specific Aim 1** is percent of time spent <54 mg/dL on CGM. With a sample size of 10 women per group (20 study completers), we will have 80% power to detect non-inferiority using a one-sided alpha of 0.025 and a non-inferiority margin of 1.5% of time spent <54 mg/dL for HCL compared to SAPT, using estimates of variability from the PI's current study of CGM use during pregnancy. The standard deviation of time spent <54 mg/dL based on data from the PI's current study of CGM use during pregnancy was 1.1%. For **Specific Aim 2**, with a sample size of 10 women per group (20 study completers), we will have 83% power to detect a difference in time spent in target glucose range (65-140 mg/dL, this range was used in the power calculations because at that time there was no consensus on optimal time in range in pregnancy) of 3.3 hours/day (13.8%) between HCL to SAPT, assuming a standard deviation of 2.5 hours/day (effect size=1.0 SD). This is similar to effect sizes reported in another artificial pancreas study showing a difference of 2.5 hours/day (10.4%) between groups and a study of HCL in pregnancy (in a crossover design) showing a difference of 3.6 hours/day (15.2%). While this study is not powered to detect significant differences in maternal-fetal outcomes as described in **Specific Aim 4**, our goal is to provide estimates and preliminary data on these outcomes to inform the sample size needed for a larger trial focused on these outcomes, once the safety of the HCL system in pregnancy has been established.

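### SA 3.1 takes a non-significant SF-36 difference as similar quality of life, with 10 women per arm and no margin; SA 1.2 shares the weakness less explicitly

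*Combined protocol and SAP*

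**What the plan says.** Hypothesis SA 3.1 (section II) predicts similar SF-36 scores in the two arms and qualifies this with "without a significant difference between groups". No other hypothesis ties similarity to a significance test.

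The matching analysis in section F, Statistical Analysis Plan, reads "we will compare SF-36 scores, insulin device satisfaction and glucose device satisfaction by group (HCL vs. SAPT) using t-tests if scores are normally distributed", with Wilcoxon rank-sum otherwise. Alpha is 0.05 for everything except the non-inferiority tests, which use 0.025. The Power and Sample Size paragraph is built on 10 completers per arm. No SF-36 margin, SD, effect size or confidence-interval criterion is given.

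For SA 1.2 the hypothesis is "We hypothesize that the episodes of diabetic ketoacidosis and rates of adverse skin reactions will be similar between groups". The analysis is "Counts of DKA and adverse skin reactions (secondary outcomes) will be compared between groups (HCL vs. SAPT) using t-tests for normally distributed variables", or Wilcoxon otherwise. The next sentence says that, because the purpose is to show a similar safety profile, a non-inferiority test will be used. The only margins in the plan are for time below 54 mg/dL. A secondary analysis of severe hypoglycemia, ketoacidosis and skin reactions uses Poisson regression with an offset for follow-up time.

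**The concern.** A difference test asks whether the data rule out zero difference. Failing to rule it out does not show that the difference is small, and with 10 women per arm such failure is likely over a wide range of true differences. If SA 3.1 is applied as worded, low precision can confirm the hypothesis.

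This matters because the device was not designed for pregnancy and, by the protocol's own account, women already use it. A report of similar quality of life or similar ketoacidosis, resting on p>0.05, could be taken as reassurance that the data do not give. The plan already accepts the principle for time below 54 mg/dL, where it sets a margin. It does not carry it through to the other outcomes that it expects to be similar.

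**Working it through.** **Inputs.** From the documents: 10 completers per arm (Power and Sample Size), up to 24 randomised (section B), alpha 0.05, t-test or Wilcoxon. Assumed: two-sided tests (sidedness is not stated), 1:1 allocation, one unadjusted comparison, and true differences of 0.5 to 1.32 SD (the documents give no SF-36 effect or SD).

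**The plan's own figures first.**
- SA 1: margin 1.5, SD 1.1, one-sided 0.025, 10 per arm gives 82.2% (t) or 86.2% (normal), against a stated 80%.
- SA 2: 3.3/2.5 = 1.32 SD gives 83.9% (normal) or 79.7% (noncentral t), against a stated 83%. The plan labels this effect 1.0 SD; at 1.0 SD power would be 60.9% (normal) or 56.2% (t).

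So 10 per arm gives about 80% power only for differences near 1.3 SD.

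**Chance of a non-significant SF-36 result.** With n per arm, df = 2n − 2 and noncentrality = d × √(n/2). At n = 10, df = 18, the critical value is 2.101 and noncentrality is 2.236 × d. The Wilcoxon column is simulated with normal data.

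| True difference (SD) | Noncentrality (n=10) | t-test, 10 per arm | Wilcoxon, 10 per arm | t-test, 12 per arm |
|---|---|---|---|---|
| 0.5 | 1.12 | 81% | 84% | 78% |
| 0.8 | 1.79 | 60% | 65% | 53% |
| 1.0 | 2.24 | 44% | 49% | 35% |
| 1.32 | 2.95 | 20% | 24% | 13% |

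The t-test is non-significant half the time at 0.93 SD with 10 per arm, and at 0.84 SD with 12.

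**Precision.** The 95% CI half-width is 2.101 × √(2/10) = 0.94 SD with 10 per arm (0.85 SD with 12). Identical observed means would leave differences up to 0.94 SD in either direction within the interval. An estimate just short of significance would have an interval from about 0 to 2 × 0.94 = 1.88 SD.

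**Could equivalence be tested instead?** Take two one-sided 0.05 tests, a true difference of zero and 80% power. Then n per arm = 2 × ((1.645 + 1.282)/margin)². Assumed margins of 0.5, 0.8 and 1.0 SD need 69, 27 and 18 women per arm. With 10 per arm, simulated power is 0.1%, 12% and 39%. Equivalence is out of reach at this size.

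**SA 1.2.** The documents give no expected rates, so a power figure would rest wholly on assumption. A bound does not. If none of 10 women in an arm had ketoacidosis, the exact 95% upper limit for the proportion affected is 1 − 0.025^(1/10) = 31%.

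**The case against.** The best case on the other side has five parts.

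1. **Only SA 3.1 names non-significance.** A reader might infer that all four hypotheses predicting similarity (SA 1.2, 3.1, 4.1 and 4.2) are to be judged that way. The documents do not support this. The other three state expectations, and the analysis plan never says that p>0.05 confirms them. This stands and limits the point. For SA 3.1 one can still say that the phrase is only a prediction, but it is the only operational meaning of similar that the plan gives.

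2. **SA 4 is already disclosed.** Hypothesis SA 4.1 reads "We hypothesize that rates of fetal loss, preeclampsia, cesarean section, and neonatal hypoglycemia will be similar between groups", and the plan examines "rates of fetal loss, preeclampsia, cesarean section, LGA, and neonatal hypoglycemia using Chi-square tests". It is tempting to conclude that cesarean or large-for-gestational-age rates would be declared similar. But the aim is labelled exploratory, and the Power and Sample Size paragraph says that the study is unpowered for these outcomes and aims to supply estimates for a larger trial. Only the intervals are missing.

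3. **The safety paragraph mentions non-inferiority.** The sentence follows directly after ketoacidosis and skin reactions, and alpha is set for non-inferiority tests in the plural. So one cannot say flatly that these outcomes get no such test. But with no margin for them, the test cannot be carried out. The Poisson analysis would yield rate ratios, though no interval or reading of them is specified.

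4. **Large differences would not always be missed.** This stands. From about 0.93 SD upward a significant result is the likelier one, and at 1.32 SD the t-test misses 20%. It would be wrong to say that non-significance is expected whatever the truth.

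5. **Safety oversight does not rest on these tests.** The monitoring board and the stopping rules in Table 5 act on event counts. This stands, and it keeps the point to inference and reporting.

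**Conclusion.** The point holds for SA 3.1. The stated mark of similarity is a non-significant difference, without a margin, at a size where true differences up to about 0.93 SD would more often than not meet it: 81% of the time at 0.5 SD and 60% at 0.8 SD. Twelve per arm changes this only modestly (78% and 53%).

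For SA 1.2 it holds in weaker form: a prediction of similarity, difference tests, and a non-inferiority sentence that lacks a margin for these outcomes. For SA 4 the documents already disclose the limitation, so no error of inference is shown there.

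The percentages rest on two-sided testing, equal allocation, normal scores and a single unadjusted comparison. Which SF-36 difference matters clinically is not in the documents, so the SD scale is an assumption. The outcomes are secondary, and the primary analysis of time below 54 mg/dL is unaffected. The correction should be made, but it is one of wording and reporting.

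**What to change.** - **SA 3.1:** delete the non-significance phrase as the criterion, and restate the hypothesis as estimation of the SF-36 difference between arms.
- **Statistical Analysis Plan, SA 3:** report HCL minus SAPT for SF-36 with a 95% CI.
- **Statistical Analysis Plan, SA 1:** report the rate ratio or rate difference for ketoacidosis and skin reactions with a 95% CI, by an exact method if an arm has no events. State that the non-inferiority sentence applies only to time below 54 mg/dL, or give margins for the other outcomes.
- **Add one sentence:** p>0.05 will not be read as similarity, and the trial is not sized to show equivalence on these outcomes.
- **SA 4:** only add CIs to the estimates already promised.

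The cost is a few sentences, with no change to sample size, visits or data collection. The trial gives up a similarity claim on SF-36, ketoacidosis and skin reactions that 10 women per arm could not support.

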### III. Background and Significance:

Pregnancies associated with type 1 diabetes (T1D) are accompanied by high risks of adverse maternal and fetal outcomes. To reduce the risk of adverse health outcomes occurring, it is recommended that women obtain and maintain tight glycemic control throughout gestation. This task is difficult given the ever-changing insulin requirements in pregnancy. The insulin-sensitive 1st trimester predisposes women to nocturnal hypoglycemia. Insulin resistance begins 14 to 20 weeks gestation because of increased placental-fetal unit demands, free fatty acid production, and placental/maternal hormonal influences. The early post-partum period cuts insulin requirements 35-90% from pre-pregnancy doses because of cessation of placental hormones. Achieving tight glycemic targets under these conditions, without causing SH, is one of the biggest challenges of diabetes pregnancy care. For women with T1D, the high stakes and strict goals of pregnancy can negatively impact QOL and mental health. CL therapy is a novel way to improve care and QOL among pregnant women with diabetes.

**CL in Pregnancy:** Three studies have been done in this field, all with crossover designs. (1) The Deltec Cozmo insulin pump and FreeStyle Navigator CGM (HCL system with a model predictive control algorithm) was worn by 10 women for 24 hours at a time at 14.8 and 28 weeks gestation. Plasma TIR (63-140 mg/dL) overnight increased (84% early to 100% in late gestation,  $p=0.09$ ), though nocturnal hypo- and hyperglycemia did not change. (2) The Animas 2020 Insulin Pump with FreeStyle Navigator CGM or CSII alone was used for 24 hours at a time at 19 and 23 weeks gestation ( $n=12$ ). Hypoglycemia was significantly reduced with HCL wear (time spent  $<45$  mg/dL, lower low blood glucose index, and fewer hypoglycemic episodes), but overnight plasma TIR was similar in both groups. Overall, both sessions were in the plasma TIR 81% of the time. (3) Finally, 16 women were randomly assigned to HCL therapy (DANA Diabecare R Insulin Pump with FreeStyle Navigator II CGM) or SAPT (control condition) for 4 weeks of over-night use then crossed over after a washout period. Women were then allowed to continue HCL therapy, if they wanted to do so. The HCL system used was investigational and utilized a model predictive control (MPC) algorithm^34. Semi-structured interviews and validated questionnaire data from this study showed that HCL wear was associated with some modest benefits with respect to quality of life (feelings of better glucose control/excitement/empowerment and less worry about hypoglycemia occurring overnight) but also concerns about device visibility and varying degrees of attention to data and hypo-/hyperglycemia symptoms. Time spent  $<63$  mg/dL was low in both groups (1.9% HCL vs 1.8% SAPT,  $p=0.67$ ). HCL wear significantly increased TIR (66.3% HCL vs 56.8% SAPT,  $p<0.001$ ), decreased time  $>140$  mg/dL (31.6% HCL vs 40.9% SAPT,  $p<0.001$ ) and  $>180$  mg/dL (12.6% HCL vs 17.3% SAPT,  $p=0.001$ ), and lowered mean glucose (128 mg/dL HCL vs 137 mg/dL SAPT,  $p<0.001$ ). After crossover, 87.5% (14/16) of the women continued using HCL therapy until delivery. There were 26 adverse events (skin reactions and minor illnesses) and 95 device deficiencies with no differences between groups. Serious adverse events were unrelated to the devices. For the 24 hours prior to delivery the median glucose level was 110 mg/dL (86.8% TIR). Adverse outcomes were: 5 cases of pre-eclampsia, 15 cesarean section deliveries (10 prior to onset of labor), 7 deliveries  $<37$  weeks gestation, 13 LGA infants (birth weight  $>90^{\text{th}}$  percentile), 14 infants with neonatal hypoglycemia, and 12 cases of neonatal intensive care admissions. Thus, hypoglycemia was reduced with one and TIR increased with two out of the three HCL systems. None of the HCL systems studied are approved in the United States. No HCL system has been compared to SAPT for the duration of a pregnancy and early post-partum or has been shown to improve maternal and fetal outcomes. None of the HCL systems studied in pregnancy used a PID control algorithm, which may perform differently

than then MPC algorithms in situations of dramatic shifts in insulin requirements such as pregnancies complicated by diabetes and the transition from extreme insulin resistance in the 3rd trimester to insulin sensitivity post-partum.

This novel study will compare the only approved HCL system (novel therapy) to SAPT (often-used therapy) throughout pregnancy and early post-partum. The FDA-approved device we will use has a proportional-integral-derivative (PID) controller, which has never been studied in pregnancy. We will assess **safety (SA 1)** by measuring: 1) SH, 2) episodes of diabetic ketoacidosis (DKA), and 3) adverse skin reactions. We will compare **indices of glycemic variability (SA 2)** and **fear of hypoglycemia (SA 2)** between groups. Pregnancy often leads to hypervigilance with self-care, but also increased emotional stress and burden. This study will assess psychological factors (**QOL, SA 3**) during and after pregnancy: QOL (SF-36) and device satisfaction (3 surveys for people with T1D). We will collect data about **maternal and fetal health outcomes (SA 4)**.

